## A. Introduction

Sarcoidosis is a systemic granulomatous disease of unknown cause, most commonly affecting the lungs, afflicting young to middle-aged adults in the prime of their lives, for which highly effective and well-tolerated therapies are lacking. First-line therapies for sarcoidosis are often ineffective, poorly tolerated and promote long-term health complications. Industry-sponsored clinical trials have tested proprietary, expensive and potentially toxic therapies that are reserved for refractory cases of sarcoidosis (1). Given that nicotine patches are FDA approved for other indications and readily available to the public without a prescription, it is unlikely that a multi-center placebo-controlled nicotine trial for sarcoidosis will ever be conducted without NIH-support. *In keeping with the NIH's goal to "repurpose" existing biologics, the proposed Clinical Trial Pilot Study will provide preliminary data required to design subsequent Phase II/III trials to evaluate nicotine as a novel low-cost, highly-effective, and safe treatment option for patients with active pulmonary sarcoidosis.* 

Nicotine may be beneficial for the treatment of pulmonary sarcoidosis. At least three independent epidemiological studies indicate that smokers and chewing tobacco users, chronically exposed to nicotine, have a ~2-fold lower risk of developing sarcoidosis (2-4). Nicotine reprograms inflammatory pathways through the actions of  $\alpha$ 7 nicotinic receptors (5), thereby inhibiting various pro-inflammatory immune responses (5,6), particularly prototypical Th1 immune responses (7,8), which are the hallmark of sarcoidosis and other granulomatous disorders. Reprogramming of Th1 immunity could explain the benefits of nicotine treatment for Crohn's disease (9) and hypersensitivity pneumonitis (10), granulomatous disorders of the intestines and lungs, respectively. Our pilot study showed that nicotine is well-tolerated, and normalizes Th1 type immune responses in patients with active pulmonary sarcoidosis (11). The specific objective of this project will determine if nicotine treatment is safe and efficacious for patients with active pulmonary disease despite conventional therapy.

## **B. Background**

Sarcoidosis is characterized by the development of non-necrotizing granulomatous inflammation in the absence of identifiable infectious or environmental causes. The disease typically involves the lungs, frequently leading to impaired exercise tolerance and associated dyspnea. A majority of patients with active pulmonary sarcoidosis complain of overwhelming fatigue, which often persists despite administration of immunemodulating drugs typically used to treat sarcoidosis (12,13). Furthermore, conventional treatments are associated with a spectrum of serious untoward effects, including diabetes mellitus, osteoporosis, bone marrow suppression, severe infections, cirrhosis, etc. (14,15). Indeed, the use of corticosteroids, the mainstay of pulmonary sarcoidosis treatment, is independently associated with a reduced quality-of-life (16). Although potent anti-TNF $\alpha$  drugs can be effective alternatives to usual care (1,14,15) they are exceedingly expensive, many insurance agencies (e.g., Medicare) and the FDA do not approve their use for sarcoidosis, and they predispose to serious complications, including the reactivation of latent TB, serum sickness, and increased risk of malignancy (17). As such, these agents are typically reserved for the treatment of refractory disease. Nicotine, through its actions on  $\alpha$ 7-nicotinic receptors, possesses potent immune-modulating actions. At higher concentrations ( $\mu$ M), nicotine suppresses antigen-mediated TNF $\alpha$  production (5,6), induces regulatory T cells (18-20), suppresses Th1 type immune responses (7,8), particularly in the lung (21,22), and, as such, is expected to suppress Th1-dependent granuloma formation. In support of a benefit in sarcoidosis, large epidemiological studies consistently show that chronic nicotine use (smoking or smokeless tobacco) reduces the risk of developing sarcoidosis (2-4). Moreover, by stimulating the dopaminergic axis of the brain, nicotine significantly improves fatigue (23) and depression symptoms (24,25), which are common (prevalence >50%),

quality-of-life-altering disease manifestations in sarcoidosis patients (16,26). Based upon these observations, and our supportive preliminary data, we hypothesize that nicotine will be an effective therapy for sarcoidosis. If shown to be effective, the contribution is significant because nicotine is already FDA approved for this application (established for our pilot study), is readily available to patients, is shown to be well-tolerated, and represents a low-cost, low-risk alternative to currently available treatments. As such, this project represents an opportunity to "**repurpose**" nicotine for a new therapeutic application.

## C. Study Objectives

**Rationale for the proposed study aims:** It should first be emphasized that this Clinical Trial Pilot Study is designed to provide preliminary clinical efficacy and safety data for the purpose of planning a subsequent definitive multi-institutional clinical trial

In terms of meaningful clinical endpoints, serial pulmonary function testing, particularly forced vital capacity (FVC) is the current objective standard for assessing disease status in patients with pulmonary sarcoidosis. Thus, changes in FVC will be considered as the primary clinical endpoint for this clinical trial. However, serial FVC measurements can vary up to 10%, and expected changes in FVC with effective therapies is typically less than 5%, necessitating larger clinical trials to demonstrate efficacy. In contrast, changes in radiographic pulmonary disease manifestations in the context of effective therapies for sarcoidosis are much greater in magnitude than FVC (27). Furthermore, changes in pulmonary radiographic disease burden are an accepted surrogate for FVC and other clinical endpoints (28-31). In this regard, we have developed an objective computerized CT image analysis tool that can detect the common manifestations of pulmonary sarcoidosis and correlates strongly with FVC (32). Of note, our new unpublished data demonstrates strong correlations between the Lung Texture Score (LTS) derived from computerized CT image analysis and lung disease severity (as reflected by FVC, total lung capacity (TLC), and lung diffusing capacity) in other interstitial lung diseases (data not shown), which further validates this novel lung CT image analysis approach. Other meaningful clinical endpoints relating to disease-specific symptoms will be considered in Aim 3. For instance, fatigue is among the most common and disabling symptoms associated with sarcoidosis, which is often refractory to conventional sarcoidosis treatments (16, 26), and there is reason to believe that nicotine treatment will attenuate these symptoms (23-25). Finally, and in the spirit of a Clinical Trial Pilot Study, Aim 4 will address drug safety and tolerance, for the purpose of planning a larger, more definitive clinical trial.

# Aim 1: Estimate study size for a definitive randomized control trial (RCT) based upon change in Forced Vital Capacity (FVC) in pulmonary sarcoidosis patients treated with transdermal nicotine for 24 weeks.

Aim 2: Determine if nicotine treatment is associated with improvement in radiographic lung disease burden in patients with pulmonary sarcoidosis.

Aim 3: Consider alternative clinical endpoints for future nicotine RCT based upon subjective clinical response to nicotine treatment in pulmonary sarcoidosis patients.

Aim 4: Determine the safety and tolerance of nicotine treatment in patients with pulmonary sarcoidosis for the design of subsequent definitive double-blinded RCT.

## D. Investigational Agent

**D1.** Preclinical Data from the Pilot Study: "Nicotine for the Treatment of Pulmonary Sarcoidosis": Our pilot study sought to determine if nicotine was well-tolerated and would restore antigen-mediated immune responses in patients with active pulmonary sarcoidosis. Nicotine was reviewed as an investigational new drug (IND) by FDA and by our local IRBs to treat sarcoidosis patients. The findings of the study are detailed in our recent publication (11). To summarize, there were no serious adverse events or signs of addiction or dependency. In keeping with previous nicotine patch studies (33), minor side effects occurring at a frequency exceeding 10% were: headaches, abnormal dreams, agitation, insomnia, and local skin irritation, which improved or resolved within weeks of treatment. There was a trend towards lower fatigue scores, but no statistically significant changes were observed in reported sarcoidosis symptoms (SHQ, FAS) or measured FVC following nicotine treatment.

Nicotine treatment was associated with normalization of peripheral blood T cell subsets. In keeping with previous studies (34), active pulmonary sarcoidosis was associated with peripheral lymphopenia, including reduced FoxP3+ regulatory T cells (Tregs). Nicotine was shown to reverse peripheral lymphopenia and restore Treg populations, particularly a CD25 subset that was recently shown to be a "pre-activated" Treg. The CD4+CD25FoxP3+ Treg subtype is interesting in that it lacks suppressive actions on effector (CD4+) T cells, becoming regulatory upon stimulation (e.g., IL-2) (35). Thus, these cells are believed to be in transit to diseased tissues whereupon they adopt suppressive activity (36).

Nicotine treatment reverses peripheral anergy. Peripheral anergy to certain antigens is a well-known feature of active pulmonary sarcoidosis, and correlates with disease severity (37). In keeping with previous studies (38,39), our data shows that patients with active pulmonary sarcoidosis are specifically anergic to TLR2, TLR4 and TLR9 ligands. Moreover, nicotine treatment restored immune responsiveness to these ligands. This data is conforms to the hypothesis that sarcoidosis is associated with blunted antigen-mediated immune responses leading to impaired antigen clearance and sustained granulomatous inflammation (40). The proposed ancillary studies will determine the mechanisms by which nicotine, and more specifically  $\alpha$ 7-nicotinic receptors, restores antigen-mediated T cell responses.

Nicotine treatment did not promote tachyphylaxis. It is interesting to note that  $\alpha$ 7-nicotinic receptor expression is dramatically increased in patients with active pulmonary sarcoidosis, which is predictive of response to nicotine (11). One concern relating to the chronic effects of nicotine was the potential development of tachyphylaxis (e.g., reduced  $\alpha$ 7-nicotinic receptor expression). No change in  $\alpha$ 7-nicotinic receptor expression on immune cells was observed in the nicotine treatment group (11).

#### D2. Clinical Data to Date

Our previous pilot study was not powered to assess clinical endpoints relating to efficacy. However, nicotine was well-tolerated in patients with pulmonary sarcoidosis. Common (>10%) minor side effects observed in our pilot study (11), and reported elsewhere (33), includes local skin irritation, headaches, nightmares, sleep disturbances, which tend to subside with ongoing therapy. There were no serious adverse effects.

#### D3. Dose Rationale and Risk/Benefits

Cigarette smokers, and smokeless tobacco users, have ~2-fold reduction in risk of developing sarcoidosis (2-4). Transdermal nicotine patch delivery systems are designed to attain *in vivo* drug levels approximating that of regular cigarette smokers, which is in the 10-40 nM range (41,42). Nicotine in this concentration, when achieved in animals, is shown to suppress T-cell mediated immune responses (43, 44). The 21 mg/day nicotine patch achieves drug levels within this range humans (41,42), and is shown to be well tolerated in terms of serious adverse events in large clinical studies (45). Furthermore, the transdermal nicotine delivery approach reduces the risk of developing dependency by providing steady nicotine levels *in vivo* (46). To the extent that nicotine levels attained in smokers prevents the development and progression of sarcoidosis, the 21 mg/day transdermal nicotine dose achieves our goal of attaining a biologically relevant dose of nicotine that will be well-tolerated in most subjects.

# E. Study Design

#### E1. Overview of Design Summary

This will be a prospective, randomized, parallel design with multiple measures, double-blinded, placebocontrolled study conducted on adults with confirmed sarcoidosis (e.g., biopsy proven, or a clinical diagnosis made by sarcoidosis experts) sarcoidosis to determine the effects of transdermal nicotine treatment in patients with active pulmonary disease despite conventional therapies. Patients will be enrolled sequentially and based solely on eligibility. Patients will be randomized in a 1:1 ratio to receive transdermal nicotine 21 mg/daily or an identical-appearing placebo patch. Baseline measurements will be made at the screening and baseline visits on all patients prior to receiving their randomized assigned treatment to a nicotine treatment group (n = 25 patients) and a control group (n = 25 patients) assigned to placebo patch treatment. Nicotine treatment will begin with a 2 week phase in during which the dose of nicotine will be increased weekly towards the highest tolerated dose, using the transdermal drug delivery approach (7 mg patch, 14 mg patch, 21 mg patch). Patients will be maintained on the highest tolerated dose (7-21 mg patch) for the duration of the 24 week treatment protocol. Nicotine treatment will then be deescalated weekly (i.e., 14 mg, 7 mg, and then discontinued).

#### E2. Subject Selection and Withdrawal

#### Inclusion and Exclusion Criteria:

Adult male and female subjects  $\geq$  18 to  $\leq$  75 years of age will be screened for eligibility. Eligible adult patients will have:

• Strong clinical evidence of sarcoidosis confirmed by the expert pulmonologists (site PIs), diagnosed at least 2 months before screening, with evidence of parenchymal disease on a recent chest radiograph

performed as part of routine clinical care or during initial screening for this study (for the purpose of research).

- A Medical Research Council dyspnea score (47) of at least grade 1
- Patients must be on no treatment or on a stable treatment regimen for sarcoidosis for at least one month prior to enrollment in the study.

Major exclusion criteria include:

- Recent (within 3 mos) treatment with an anti-TNFalpha therapy (infliximab, adalimumab, etanercept, etc).
- Active tobacco smoking or use of smokeless tobacco products containing nicotine
- Active cardiac or central nervous system disease
- History of adverse reaction to nicotine or nicotine-containing products
- Patients with extensive irreversible pulmonary fibrosis (based upon lung biopsy or high resolution CT scan criterion)
- Inability to provide consent.
- The subject will be excluded if they have recently smoked (within 6 months) or have a diagnosis of other significant respiratory disorder other than sarcoidosis that in the opinion of the investigator would complicate the evaluation of response to treatment.
- History of substance abuse (drugs or alcohol) within 3 years prior to screening or other circumstances (e.g., psychiatric disease) that could interfere with the subject's adherence to protocol requirements or increase their risk of drug (nicotine) dependence.
- Patients with a diagnosis of current or recently active cancer (within 1 year) will be excluded.
- Pregnant women will be excluded

*Ethical Considerations:* Enrollment will be restricted to adults who are capable of providing informed consent and will be unbiased to race, gender or economic status. To avoid any risk of coercion, we will not recruit prisoners.

Subject Recruitment Plans and Consent Process: Patients will be enrolled sequentially and based solely on eligibility. Consent will be obtained by experienced research coordinators under the direct supervision of the site PI at each clinical site and only after obtaining written, informed consent. Subjects who are successfully screened will be assigned a subject number.

We will leverage existing CTSA (NIH) supported resources. For instance, we will utilize OSU's CTSAsponsored "Research Match" program, a secure volunteer registry for prospective study participants, to screen for potential study subjects and subjects will be able to actively seek the study using the "StudySearch" tool that lists research studies and clinical trials at The Ohio State University that are actively seeking participants. Additional advertising of the study will be available by entering the study into the ClinicalTrials.gov registry.

If, during the screening phase, the subject has a clinically significant worsening of sarcoidosis requiring adjustment of baseline medications, the subject will be considered a screen failure and is not eligible for randomization at that time. In this case, the subject may be rescreened after appropriate treatment has been given, and the subject has been on a stable dose of the medication for at least 4 weeks.

An informed consent form will be prepared according to the institutional requirements for informed consent and the applicable regulations. A sample consent form from the related pilot study (11) is provided in the Appendix. The appropriate IRB must approve the protocol and informed consent documents, agree to monitor the conduct of the study, and agree to review study progress periodically, at intervals not to exceed 1 year. To this end, the two Clinical and Translational Science Award (CTSA) institutions engaging in this study from Ohio (Ohio State University and Cleveland Clinic Foundation) have established a statewide collaborative agreement allowing a single IRB, in this case Ohio State University's, to assume IRB responsibilities on behalf of multiple institutions when conducting multicenter studies. This collaborative arrangement will serve to accelerate research by streamlining human subject protection processes.

The consent form will be reviewed with the prospective study subject or his/her legal representative, and the investigator will be available to answer questions regarding procedures, risks, and alternatives. The principal investigator or his/her entitled designee (as defined on the Delegation List) will obtain written informed consent from each subject or from the subject's legal representative or designee. Consent will be obtained before any protocol-specific procedures are performed. Documentation of the subject's informed consent for and participation in this study will be noted in the subject's medical record. If the subject is enrolled in the ancillary study relating to this protocol, a sub study-specific consent must also be used. The subject or his/her legal representative must be provided with a copy of the consent form for the main study and a copy of any separate consent form for the sub study (if applicable).

Randomization Method and Blinding: Patients will be randomized to nicotine or placebo in a 1:1 ratio. Randomization will be within each site (balanced by site) and use permuted blocks of varying size (2,4,6). The randomization scheme will be developed by the study statisticians and the scheme allocated through the blinded study subject number. Study drug will be pre-packaged with an assigned study subject number, corresponding to the allocated randomized treatment. All baseline measurements will be obtained at the screening and baseline visit before allocation of the random assignment. Identically labeled nicotine and placebo patches will be randomly designated treatments "A" or "B", and will be distributed by each clinical center.

*Risks and Benefits:* Nicotine intolerance rates are very low, even at doses 2-fold greater than the maximum dose used in this study (48). Common (>10%) minor side effects observed in our pilot study (11), and reported elsewhere (33), includes local skin irritation, headaches, nightmares, sleep disturbances. We are aware of the potential for serious adverse events, particularly cardiac arrhythmias (49) and seizures (50) in patients with underlying heart or central nervous system disease, respectively, and will exclude patients with these risk factors from enrollment in this study.

*Early Withdrawal of Subjects:* Patients will be immediately withdrawn from the clinical trial for any of the following reasons: 1) at the request of the subject, 2) at the discretion of clinicians caring for the patient, 3) as

advised by the DSMB, 4) if the subject is unable to comply with the study protocol. The Research Manager will be notified within 48 hrs of the subject's withdrawal and will record the reason for withdrawal.

Data Collection and Follow-up for Withdrawn Subjects: Withdrawn subjects will be encouraged to return for the post intervention study-related procedures, including image analyses, surveys, and PFTs, in order to include them in analysis, following the intention-to-treat principle.

#### E3. Study Drug

Description: Sustained release transdermal nicotine (7, 14 and 21 mg daily dose patches) and matching placebo patches will be provided. The nicotine patches and matching control patches will be administered daily according to the manufacturer's recommendations and in compliance with a FDA approved dosing regimen.

Treatment Regimen: To optimize patient compliance and minimize side-effects, nicotine (or matching placebo patch) treatment will be initiated at 7 mg/day and escalated at weekly intervals to 14 mg/day, then 21 mg/day, as tolerated. If intolerance develops, the dose will be reduced to the highest tolerated dose. The dose will be maintained at 21 mg/day (or the highest tolerated dose) for 24 weeks, at which time the dose will be deescalated to 14 mg/day, then 7 mg/day at weekly intervals, after which nicotine treatment will be discontinued.

Method for Assigning Subjects to Treatment Groups: Patients will be randomized to nicotine or placebo patches in a 1:1 ratio. The randomization scheme will be developed by the study statisticians and the scheme allocated through the blinded study subject number. Study drug will be pre-packaged with an assigned study subject number, corresponding to the allocated randomized treatment. Treatment allocations will be blinded to study clinical staff, treating clinicians and patients. Nicotine and replica placebo patches will be randomly designated treatments "A" or "B", and will be distributed by each clinical center. All baseline measurements will be obtained at the screening and baseline visit before allocation of the random assignment

Preparation and Administration of Study Drug: Patients will be instructed to apply a new patch to their skin every day. The site should be clean (e.g., with warm soapy water) and dry at the time of application and only one patch should be placed at a time (old patches must be removed before applying a new one). The backing of the patch is removed to reveal the sticky surface, which is placed on the skin. To avoid local skin irritation, a new site is recommended (e.g., on the upper arm) each day.

Subject Compliance Monitoring: Subject compliance with nicotine will be monitored by history and objectively at regular intervals, as reflected by measuring nicotine and cotinine, a stable nicotine metabolite, as per the Study Schedule of Events (Table 1), described below.

Prior and Concomitant Therapy: As described in the Inclusion Criteria, above, study subjects will remain on prior and concomitant medications (if applicable), as tolerated, for the duration of the study. The addition of new medications or changes in current medication doses will be considered a violation of the study protocol. However, the patients will be retained in the study to consider trends in de-escalation or escalation of treatment in the treatment and placebo groups.

Packaging and Blinding: The packaging of the nicotine patches and placebo patches will be identical in appearance such that the patients and research staff remain blinded to treatment. Identically labeled nicotine and placebo patches will be randomly designated treatments "A" or "B", and will be distributed by each clinical center.

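### One taper (14 mg, 7 mg, stop) is given for every permitted maintenance dose, but it steps down throughout only from 21 mg; from 7 mg its first step is upward

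*Combined protocol and SAP*

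**What the plan says.** Section E3 (Study Drug, Treatment Regimen) supplies three patch strengths: "Sustained release transdermal nicotine (7, 14 and 21 mg daily dose patches) and matching placebo patches will be provided". Treatment is "initiated at 7 mg/day and escalated at weekly intervals to 14 mg/day, then 21 mg/day, as tolerated". The rule for patients who cannot go on is: "If intolerance develops, the dose will be reduced to the highest tolerated dose".

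Section E1 confirms that maintenance below 21 mg is part of the plan: "Patients will be maintained on the highest tolerated dose (7-21 mg patch) for the duration of the 24 week treatment protocol".

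The taper appears twice. In E3, the sentence that begins with maintenance at 21 mg/day brings lower doses in by a parenthesis and then gives one sequence: "or the highest tolerated dose) for 24 weeks, at which time the dose will be deescalated to 14 mg/day, then 7 mg/day", at weekly intervals, then off. E1 gives the same sequence: "Nicotine treatment will then be deescalated weekly (i.e., 14 mg, 7 mg, and then discontinued". Neither section gives a separate sequence for patients maintained at 14 mg or 7 mg. Table 1 (Study Schedule of Events) has one de-escalation column, weeks 26-28, for everyone.

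**The concern.** The plan allows three maintenance doses, but the taper it lists fits only the highest. The parenthesis in E3 puts patients on a lower dose within the sentence, so the problem is not just that they are left unmentioned: they are included, and the steps named do not work for them.

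A patient is at 7 mg because escalation went only as far as was tolerated, or because the dose was brought back down. For that patient the listed first step lies above the dose the plan itself treats as the highest tolerated.

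Two things are at stake. The first is safety in patients who have already shown intolerance. The second is Aim 4, which concerns safety and tolerance and is meant to inform the next trial. Section F3 collects adverse events through week 34 and analyses safety by treatment received, so events following an unplanned step up would be counted with the rest of the nicotine group's tolerance data. There is also a practical side. Study drug is pre-packaged by subject number and two centres take part, so staff who meet this case have no common rule to follow.

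**Working it through.** **Inputs.** Patch strengths, escalation, intolerance rule and taper: E3. Permitted maintenance range, phase-in and taper: E1. De-escalation window: Table 1.

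**Timeline, reproducing the plan's own figure.** E1 states: "Nicotine treatment will begin with a 2 week phase in".
- Start of taper: 2 weeks of phase-in + 24 weeks of maintenance = week 26.
- End of taper: week 26 + 2 weekly steps (14 mg, then 7 mg) = week 28.

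This agrees with the weeks 26-28 column in Table 1, so the timing is consistent and the problem lies only in the steps.

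**Listed taper applied to each permitted maintenance dose (mg/day).**

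| Maintenance | Weeks 26-27 | Weeks 27-28 | After week 28 | First-step change |
|---|---|---|---|---|
| 21 | 14 | 7 | 0 | 14 - 21 = -7 |
| 14 | 14 | 7 | 0 | 14 - 14 = 0 |
| 7 | 14 | 7 | 0 | 14 - 7 = +7 (14/7 = 2-fold) |

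The sequence is a reduction at every step only in the first row. In the second row, the first taper week is one more week at a dose already tolerated. In the third, the first week is a doubling.

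**Set against the plan's other statements.** The third row conflicts with the verb used in both E1 and E3, since a move from 7 to 14 mg is not a de-escalation. It also conflicts with the intolerance rule in E3, which is not limited to the phase-in.

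**How many patients.** The documents give no rate of dose-limiting intolerance, so this cannot be computed. In a nicotine arm of 25, each patient is 1/25 = 4% of the arm. Purely as an assumption, if 10-20% of the arm were held below 21 mg, that would be 0.10 x 25 = 2.5 to 0.20 x 25 = 5 patients. That count includes those at 14 mg, who face no rise. The 7 mg subset is smaller by an unknown amount and could be zero or one.

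**The case against.** The best reply is that nobody would raise the dose. The E3 sentence starts from 21 mg, the verb is de-escalate, and the intolerance rule comes immediately before it. Staff would see what was meant. This stands as to intent: a reader might infer that the protocol orders a dose increase in intolerant patients, and the documents do not support that. It does not remove the fault, because the sentence includes the lower doses and no alternative sequence is given anywhere.

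Second, few patients would be involved. Section E2 (Risks and Benefits) describes intolerance as very uncommon, and Section F3 reports one withdrawal for skin irritation in the pilot. This also stands. It is tempting to read the 2.5 to 5 patients in the working as the number facing an increase, but that figure rests on an assumed rate and counts everyone below 21 mg.

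Third, the taper weeks are not unmonitored. A reader of Table 1 could infer that they are, since the de-escalation column shows no marks as extracted. However, compliance and adverse events, vital signs, ECG and medication review are marked at week 26, and adverse events again at follow-up. F2 adds monthly calls, and F3 requires reporting through week 34. Table 1 was also read by machine, so an empty cell is weak evidence. What remains is that none of these checks is tied to the one-week step.

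Fourth, E3 refers to the manufacturer's instructions and an approved regimen. Those are not in the documents, so whether they settle the taper from lower doses cannot be checked. A general reference of that kind does not displace specific steps stated in the same section.

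**Conclusion.** The concern holds in a limited form. E1 and E3 permit three maintenance doses and give all of them one taper, which is a stepwise reduction only from 21 mg. From 14 mg the first step is no change. From 7 mg it is a rise of 7 mg/day for about one week, at odds with the word used and with the intolerance rule. This is more than a missing detail, because a stated dosing instruction contradicts itself for a group the plan provides for.

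Its reach is small. Only patients held at 7 mg would face an increase, their number cannot be derived, and it may be very few or none.

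A reader might also infer that efficacy is affected. Table 1 does not support that: PFTs and CT are tabled at week 26, when the taper has yet to begin. This rests on the timeline of E3 and Table 1. E1's 24 weeks could be read as including the phase-in, which would move the start of the taper, but the step from 7 to 14 mg would be the same.

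The effect is therefore on patient safety and on about one week of Aim 4 tolerance data. The case for correcting it rests on the kind of error and the low cost, not on how often it would arise.

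**What to change.** Reconcile the taper sentences in E1 and E3 with the highest-tolerated-dose rule, so that the taper is stated for each permitted maintenance dose (21, 14 and 7 mg), and bring the dispensing instructions into line. What the steps should be is for the sponsor's clinicians to set; this review proposes none.

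The cost is a sentence or so in each of the two sections and a matching dispensing instruction. No patients, visits or procedures are added. The small downside is that dispensing instructions would differ by maintenance dose.
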